4.2.3.3 Physical Examination

Abnormal physical examination findings before the first dose will be recorded in the medical history. Any new or aggravated clinically relevant abnormal medical finding at a physical examination as compared with the baseline assessment will be reported as an AE unless unequivocally related to the disease under study.

4.2.3.4 ECG

The observed value, the change from baseline and the percentage change from baseline will be summarised for ECG parameters by analysis visit. Box plots for the absolute and change from baseline values will be provided by analysis visit. A shift table of categorical ECG interpretation (normal, abnormal) at baseline versus end of treatment will be provided. The post-dose assessments will also be presented.

The number and percentage of patients with absolute QTcF interval prolongation (>450 ms, >480 ms, >500 ms) and QTcF increase from baseline categories (>30 ms, >60 ms, >90 ms) at any time during treatment will also be summarised.

The ECG data will be listed and any assessments performed on or after a patient took osimertinib after crossing over from 300 mg bid + placebo to 300 mg bid + osimertinib will be flagged.

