Early Phase Oncology Statistical Analysis Plan

Study Code D5084C00007

Edition Number 7.0

Date 03/07/2024

2	6	36	C2D8	33-39	C2D5-C2D11	C2D25			C2D8	
2	7	43	C2D15	40-46	C2D12-C2D18	C2D26-C3D25	43-70	64-105	C2D15	C3D1 [d]
2	8	50	C2D22	47-53	C2D19-C2D25				C2D22	
3	9	57	C3D1	54-60	C2D26-C3D4				C3D1	
3	10	64	C3D8	61-67	C3D5-C3D11				C3D8 [e]	
3	11	71	C3D15	68-74	C3D12-C3D18				C4D1 [d]	
3	12	78	C3D22	75-81	C3D19-C3D25				C4D1 [d]	
4	13	85	C4D1	82-88	C3D26-C4D4		71-98	99-126		
4	14	92	C4D8	89-95	C4D5-C4D11					
4	15	99	C4D15	96-102	C4D12-C4D18	C3D26-C4D25				

4	16	106	C4D22	103-109	C4D19-C4D25		106-147		
5	17	113	C5D1	110-116	C4D26-C5D4	C4D26-C5D25		C5D1 [d]	C5D1 [d]
5	18	120	C5D8	117-123	C5D5-C5D11				
5	19	127	C5D15	124-130	C5D12-C5D18				
5	20	134	C5D22	131-137	C5D19-C5D25				
				Etc. for Cycles 6 and above					After Week 24, tumour assessments will be every 8 weeks [c]

[a] Measurements collected before the first dose of study treatment/randomisation on Day 1 are pre-dose values and measurements collected after first dose of study treatment/randomisation on Day 1 are post-baseline values. For ePRO questionnaires, the baseline is defined as the non-missing assessment collected at Day 1, as it is assumed it is taken prior to start of the study treatment. If an assessment is missing at Day 1, the prior non-missing assessment will be used as baseline.

[b] The Week 24 window would start approximately halfway through a 6-week period and end halfway into an 8-week period, i.e. Day 196. Week 32 window will be Day 197-252, etc.

[c] For assessments occurring every 12 weeks, the same schedule should be used, i.e. for the first assessment on Day 84 the window will be Day 1-126, for the second assessment on Day 168 the window will be Day 127-210, etc.

[d] The target day will be the study day at CXD1

[e] The target day will be the study day at C3D8

The treatment discontinuation visit should occur within 7 days of the final dose of the last study treatment. For the 28-day follow-up visit a 7-day window is allowed, i.e., it should occur 21-35 days following discontinuation of both study treatments.

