3.2.2.5 Electrocardiogram Changes

Electrocardiograms [ECG] will be collected centrally. Triplicate 12-lead ECGs will be obtained at Screening, weekly in Cycle 1, Day 1 in every subsequent cycle and treatment discontinuation, using an

ECG machine that automatically calculates the heart rate and measures, PR, QRS, QT, and QTcF intervals. A 28-day follow-up assessment will only be required if an on-treatment assessment was abnormal at the time of study treatment discontinuation.

Triplicate ECGs are required to support PK sampling timepoints. As such, triplicate ECGs will be required on Cycle 3 Day 1 pre-dose, at 1 hour (h), 3 h, 4 h, and 6 h post-dose to coincide with collection of blood samples for assessment of PK of osimertinib and savolitinib at this visit.

Categorical ECG interpretation (normal, abnormal) and whether clinically significant will also be provided.

Absolute and percentage change from baseline in ECG variables will be calculated for each post-baseline visit.

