4.2.3.5 Vital Signs

The observed value, the change from baseline and the percentage change from baseline will be summarised for vital signs by analysis visit. Box plots for the absolute and change from baseline values will be provided by analysis visit. Furthermore, shift plots of baseline value versus minimum/maximum observations on study treatment will be produced.

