4.2.3.6 Laboratory Data

The observed value, the change from baseline and the percentage change from baseline for haematology and clinical chemistry will be summarised by analysis visit using descriptive statistics. For all laboratory variables the CTCAE grade including shift from baseline to maximum post-baseline grade on treatment will be summarised. Box plots for the absolute and change from baseline values of haematology and clinical chemistry parameters will be provided by analysis visit. Moreover, clinically important changes in haematology and clinical chemistry parameters will be presented based on CTCAE grade changes to 3 or 4.

Categorical urinalysis dipstick parameters (glucose, protein, blood and leukocyte esterase) will be summarised in shift tables comparing the maximum value during treatment with baseline value. Myoglobin will be listed only.

A listing of ALT, AST, total bilirubin and ALP laboratory results will be provided for all patients with potential Hy's law by visit. Individual data will also be plotted. Potential Hy's law will be based on the liver forms.

Summary table of transaminase elevation cases will be produced. Figure of ALT/AST versus total bilirubin, expressed as multiples of ULN will also be produced. These summaries will be based on the laboratory data.

The laboratory data will be listed and any assessments performed on or after a patient took osimertinib

after crossing over from 300 mg bid + placebo to 300 mg bid + osimertinib will be flagged.

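### Categorical ECG interpretation is tabulated only from baseline to end of treatment, so a transient non-QTcF abnormality is not counted per patient in any specified ECG summary

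*SAP*

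**What the plan says.** SAP 4.2.3.4 gives the ECG outputs. Numeric parameters get by-visit statistics and box plots. For the interpretation, "A shift table of categorical ECG interpretation (normal, abnormal) at baseline versus end of treatment will be provided", and the next sentence adds: "The post-dose assessments will also be presented". Patients are counted at any time during treatment for QTcF thresholds and QTcF increases only. All ECG data are listed.

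SAP 3.2.2.5 shows that more is collected than the shift table uses: "Categorical ECG interpretation (normal, abnormal) and whether clinically significant will also be provided". It also sets the schedule: "Triplicate 12-lead ECGs will be obtained at Screening, weekly in Cycle 1, Day 1 in every subsequent cycle and treatment discontinuation".

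The neighbouring safety sections work from extremes:

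- Laboratory CTCAE grades (4.2.3.6): "shift from baseline to maximum post-baseline grade on treatment will be summarised".
- Categorical dipstick results (4.2.3.6): they "will be summarised in shift tables comparing the maximum value during treatment with baseline value".
- Vital signs (4.2.3.5): "shift plots of baseline value versus minimum/maximum observations on study treatment will be produced".

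SAP 3.1.3 already has a rule for extreme-value summaries, which takes in every post-baseline value, scheduled or not. For categorical values repeated on one day it takes the worst.

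**The concern.** A shift table with one post-baseline time point shows who was abnormal at that point. It does not show who was ever abnormal on treatment. For laboratory, vital-sign and QTcF data the SAP chose outputs that pick up a transient change. For ECG interpretation it did not, and it gives no reason. The table also drops the clinical-significance flag, although that flag is collected.

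At stake is a descriptive safety count for rhythm, conduction and morphology findings that QTcF does not define. No endpoint, stopping rule or inference depends on it.

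**Working it through.** This is mainly a question of which outputs are specified. The plan states no figure to reproduce.

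**1. Outputs side by side**

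| Data | Specified summary | Post-baseline values used |
|---|---|---|
| Laboratory CTCAE grade (4.2.3.6) | shift per patient | maximum grade on treatment |
| Dipstick urinalysis (4.2.3.6) | shift per patient | maximum during treatment |
| Vital signs (4.2.3.5) | shift plot | minimum and maximum on treatment |
| QTcF (4.2.3.4) | patient counts by threshold | any time during treatment |
| Numeric ECG parameters (4.2.3.4) | group statistics, box plots | by analysis visit |
| ECG interpretation (4.2.3.4) | shift per patient | end of treatment only |

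**2. A test case.** Take a patient with a normal baseline, a conduction abnormality at Cycle 1 Day 8 with QTcF below every threshold, and a normal ECG at end of treatment. In the shift table the patient is normal-to-normal, and the QTcF counts do not include the patient. Any change in PR or QRS enters the by-visit group statistics. The interpretation itself appears only in the listing. No specified ECG summary counts this patient.

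**3. The post-dose sentence.** It has two possible meanings. In SAP 3.2.2.5, post-dose refers to the 1, 3, 4 and 6 hour readings on Cycle 3 Day 1. SAP 2.3 (Table 4, item 7.04) and 3.2.6.1 (Table 11) use the word for any assessment after treatment has started. On the narrow meaning it adds one day. On the broad meaning on-treatment interpretations may be shown in some form, but no format is given and no worst-case count is specified.

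**4. End of treatment.** The SAP does not define it. It may be the discontinuation visit, which SAP 3.2.2.5 schedules and SAP 3.1.3 times as follows: "The treatment discontinuation visit should occur within 7 days of the final dose of the last study treatment". It may instead be the last on-treatment assessment, because 3.1.3 slots the discontinuation visit into the ordinary analysis visits and does not keep it separate. On the first reading, patients with treatment ongoing at data cut-off (a disposition category in SAP 4.2.1) have no post-baseline value in the table. On the second they are included. Either way, one post-baseline time point is used.

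**5. Schedule count.** Count Cycle 1 Day 1 as baseline. For a patient who completes k cycles and then discontinues:

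scheduled post-baseline ECG days = 3 (Cycle 1 Days 8, 15, 22) + (k − 1) (Day 1 of Cycles 2 to k) + 1 (discontinuation) = k + 3

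This gives 5 for k = 2, 6 for k = 3, 9 for k = 6 and 15 for k = 12. The shift table uses one of these days. This describes the schedule; it does not measure how many patients are affected.

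**The case against.** The best reply is that the cases that matter are already counted elsewhere.

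- Protocol 8.2.4 has clinically significant on-treatment ECG abnormalities recorded as adverse events, and SAP 4.2.3.2 tabulates these per patient.
- QTc prolongation is an adverse event of special interest (Protocol 8.3.13), and QTcF outliers are counted at any time.
- PR and QRS are summarised by visit, which bears on conduction.
- SAP 3.2.2.3 has ECG data medically reviewed for other significant adverse events.

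The comparison with laboratory and vital-sign data is also imperfect. Protocol 8.3.7 keeps most deterioration in those out of adverse event reporting and does not name ECGs in that restriction, so extreme-value tables fill a gap there that is smaller for ECG.

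Most of this stands, and it is why the point is minor. Two things remain. Abnormalities judged not clinically significant have no per-patient count. And adverse event tables are not a clean count of abnormal ECGs: under Protocol 8.3.7, when an ECG change comes with symptoms, the symptom is the reported event and the ECG is supporting information.

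A reader might infer that clinically significant arrhythmias go uncounted. The documents do not support that, given the adverse event route. A reader might also infer that the table leaves out patients still on treatment at the cut-off. That follows only if end of treatment means the discontinuation visit, which the SAP does not say.

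**Conclusion.** The point holds as a minor reporting gap. The specified ECG outputs contain no any-time or worst-case patient count of abnormal interpretation. The loss is mainly transient non-QTcF abnormalities judged not clinically significant, plus a count within the ECG tables of those judged significant. The exclusion of ongoing patients is conditional on an undefined term.

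The size cannot be derived, because the documents give no rate of transient abnormal interpretations. A reader might take the schedule count to mean that a large share of patients would be missed. That depends wholly on assumption. If every new abnormality persists to the final ECG, 0% are missed. If abnormal calls are independent between ECG days with an assumed daily probability q, then for six cycles and a normal baseline the share is (1 − (1 − q)^8)(1 − q), which is 7.6%, 14.6% and 32.0% for q = 1%, 2% and 5%. These percentages include QTcF-driven and clinically significant calls that are counted elsewhere, so even on their own terms they overstate the gap. They should not be read as an estimate.

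**What to change.** In SAP 4.2.3.4:

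- Keep the existing shift table and state whether end of treatment is the last on-treatment assessment or the discontinuation visit.
- Add a shift from baseline to worst on-treatment interpretation with three levels: normal; abnormal, not clinically significant; abnormal, clinically significant.
- Use all scheduled and unscheduled on-treatment ECGs under the extreme-value rule in SAP 3.1.3, and cut savolitinib plus placebo data at crossover as in SAP 3.1.1.
- State which readings the post-dose sentence covers.

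The cost is a few sentences and one table program. Interpretation and clinical significance are already collected.

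The downside is that repeated readings add nonspecific abnormal calls, more so with longer exposure. Under the same illustrative assumption, 1 − (1 − q)^9 gives 8.6%, 16.6% and 37.0% of patients called abnormal at least once. The split by clinical significance limits this, and its significant row will partly overlap with the adverse event tables.

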4.2.3.5 Vital Signs

The observed value, the change from baseline and the percentage change from baseline will be summarised for vital signs by analysis visit. Box plots for the absolute and change from baseline values will be provided by analysis visit. Furthermore, shift plots of baseline value versus minimum/maximum observations on study treatment will be produced.

4.2.3.6 Laboratory Data

The observed value, the change from baseline and the percentage change from baseline for haematology and clinical chemistry will be summarised by analysis visit using descriptive statistics. For all laboratory variables the CTCAE grade including shift from baseline to maximum post-baseline grade on treatment will be summarised. Box plots for the absolute and change from baseline values of haematology and clinical chemistry parameters will be provided by analysis visit. Moreover, clinically important changes in haematology and clinical chemistry parameters will be presented based on CTCAE grade changes to 3 or 4.

Categorical urinalysis dipstick parameters (glucose, protein, blood and leukocyte esterase) will be summarised in shift tables comparing the maximum value during treatment with baseline value. Myoglobin will be listed only.

A listing of ALT, AST, total bilirubin and ALP laboratory results will be provided for all patients with potential Hy's law by visit. Individual data will also be plotted. Potential Hy's law will be based on the liver forms.

Summary table of transaminase elevation cases will be produced. Figure of ALT/AST versus total bilirubin, expressed as multiples of ULN will also be produced. These summaries will be based on the laboratory data.

The laboratory data will be listed and any assessments performed on or after a patient took osimertinib

after crossing over from 300 mg bid + placebo to 300 mg bid + osimertinib will be flagged.

5 INTERIM, FUTILITY, PRIMARY AND FINAL ANALYSES

Interim analysis 1 was planned to assess ORR and discontinuations due to AEs. This was to occur after approximately **CCI** patients treated with osimertinib (80 mg od) and savolitinib (300 mg od) had the opportunity to be treated for **cc1** post-baseline scans (12 weeks) or **CCI** patients treated with osimertinib (80 mg od) and savolitinib (300 mg od) had the opportunity to be treated for 6 weeks, whichever was later. To evaluate the safety and tolerability of savolitinib in combination with Osimertinib continuous monitoring of the discontinuation due to AE rate and the discontinuation due to a hypersensitivity/anaphylaxis AE rate was to be performed after **CCI** patients treated with osimertinib (80 mg od) and savolitinib (300 mg od) had the opportunity to be treated for 6 weeks up to Interim Analysis [AI]1.

Interim analysis 2 was planned to assess ORR after approximately **cc1** post 1L patients treated with osimertinib (80 mg od) and savolitinib (300 mg od) had the opportunity to be treated for **cc1** postbaseline scans (12 weeks). Recruitment was not to be paused whilst the patients required for the interims were evaluated.

A futility analysis for savolitinib + placebo arm is planned after **CCI** patients have been randomised under CSP version 7.0 and have had an opportunity to have **cc1** post-baseline scans (12 weeks). The futility rule is defined as no responses observed among the first **cc1** randomised savolitinib + placebo arm patients who have had the opportunity for **cc1** post-baseline scans, assessed by investigator.

- If true savolitinib mono response rate = **CCI** there is a **CCI** probability of observing no responses out of the first **cc1** savolitinib + placebo patients.
- If true savolitinib mono response rate = **CCI** there is a **CCI** probability of observing no responses out of the first **cc1** savolitinib + placebo patients.
- If true savolitinib mono response rate = **CCI** there is a **CCI** probability of observing no responses out of the first **cc1** savolitinib + placebo patients.

Recruitment will not be paused during the futility analysis. If the decision is made that treatment with savolitinib + placebo is futile, further enrolment into the savolitinib + placebo arm will be stopped, all randomised patients will be unblinded, and those randomised to savolitinib + placebo will be given the opportunity to cross over to savolitinib + osimertinib. Recruitment to the savolitinib + osimertinib arm will continue regardless of the results of futility analysis until the planned sample size for the savolitinib + osimertinib arm is reached.

The primary (ORR) analysis for the study will be performed at 6 months after the last patient under CSP version 7.0 has been randomised to treatment. The final analysis for the study will be performed at 15 months, after the last patient under CSP version 7.0 has been randomised to treatment.

Additional analysis for patients enrolled prior to CSP version 7.0 may be performed, if required.

6 CHANGES OF ANALYSIS FROM PROTOCOL

Although not specified in the current CSP version 7.0, Change in tumour size by investigator assessment in accordance with RECIST 1.1, best percentage change in TL tumour size, CNS ORR and CNS DoR by BICR assessments in accordance with RECIST 1.1 have been considered of interest for this study and will be explored.

Moreover, OS and PFS timepoints will be extended compared to CSP version 7.0 requirements.

DoR, PFS by investigator assessment in accordance with RECIST 1.1 will be assessed for CAS. Although present in CSP version 7.0 endpoints, DoR and PFS by ≥ 3 line of treatment will not be explored in this statistical analysis. Baseline assessments related to RECIST 1.1 will not follow CSP version 7.0 definition where 28 days window is required.

Finally, IUO grade status has been introduced. At this regard, ORR, DoR, PFS by investigator will be assessed in accordance with RECIST 1.1 using retrospective IUO grade MET testing on TPAS, SAF and CAS.

8 APPENDICES

Appendix A Subgroup Analysis list

	ORR and PFS	
	TPAS	SAF*
Race		
Asian	X	X
Non-Asian		
Sex		
Male	X	X
Female		

Age group	X	X
<65 years		
>=65 years		
Line of treatment		
2nd line		X
>=3rd line		
Missing		
Prior platinum-based chemotherapy		
Yes		X
No		
Missing		
Prior platinum-based chemotherapy and line of treatment		
Yes and 2nd line		
Yes and >=3rd line		X
No and 2nd line		
No and >=3rd line		
Missing		
Immediately prior line of therapy		
Osimertinib		
Platinum-based chemotherapy		X
Other		
Missing		

Response to immediately prior line of therapy		
Yes and osimertinib		
Yes and platinum-based chemotherapy		
Yes and other		X
No and osimertinib		
No and platinum-based chemotherapy		
No and other		
Missing		
Immediately prior line osimertinib		
Osimertinib		
Not osimertinib		X
Missing		
Response to immediately prior line of therapy, osimertinib		
Yes and osimertinib		
Yes and not osimertinib		
No and osimertinib		X
No and not osimertinib		
Missing		
Number of previous EGFR TKI therapies		
1		
2		X
...		
Missing		
T790M status in baseline plasma	X	X
T790M+		
T790M-		

C797S mutation in baseline plasma		
C797S+	X	X
C797S-		
FISH+ allocation status		
Amplified (i.e., MET/CEP7 RATIO ≥ 2)	X	X
Polysomy (i.e., MET/CEP7 RATIO < 2)		
Missing		
IHC+ allocation status		
IHC90+		
IHC90 negative (FISH10+)	X	X
IHC50+		
IHC50 negative (FISH5+)		
IHC missing/unknown (FISH positive to enter study)		
FISH+ allocation status		
FISH 10+		
FISH 10 negative (IHC90+)	X	X
FISH 5+		
FISH 5 negative (IHC50+)		
FISH missing/unknown (IHC+ to enter study)		
Overall disease classification		
Metastatic	X	X
Locally advanced		
Missing		
EGFR mutation status [d]		
Exon 19 deletion	X	
L858R		

Known or treated brain metastases at study entry		X	
Yes (present at baseline or not present at baseline but with known or treated history)		X	
No (not present at baseline and not known or treated history of brain metastases)			
ECOG at baseline	0	X	
	1		
...			
Histological type		X	
Adenocacinoma			
Other			

* SAF : savolitinib 300 mg od + osimertinib (FISH10+ and/or IHC90+)

	OS		
	TPAS	SAF*	CAS
IHC+ allocation status			
IHC90+			
IHC90 negative (FISH10+)			
IHC50+	X	X	X
IHC50 negative (FISH5+)			
IHC missing/unknown (FISH positive to enter study)			
FISH+ allocation status			
FISH 10+			
FISH 10 negative (IHC90+)	X	X	X
FISH 5+			
FISH5 negative (IHC50+)			
FISH missing/unknown (IHC+ to enter study)			

* SAF : savolitinib 300 mg od + osimertinib (FISH10+ and/or IHC90+)

Appendix B Pharmacokinetic parameter presentation rules

Parameter Symbol	Definition	Reporting in Summary Tables	Reporting in Listings
Ae	Cumulative amount of unchanged drug excreted into urine	mean/SD/med = 4 s.f min/max = 3 s.f	3 s.f
AUC _{0-t}	Area under the plasma concentration-time curve from time zero to time t	mean/SD/Geomean/CV/GeomeanSD/med = 4 s.f. min/max = 3 s.f	3 s.f
AUC _τ	Area under the plasma concentration-time in the dose interval	mean/SD/Geomean/CV/GeomeanSD/med = 4 s.f. min/max = 3 s.f	3 s.f
AUC	Area under the plasma concentration-time curve from zero to infinity	mean/SD/Geomean/CV/GeomeanSD/med = 4 s.f. min/max = 3 s.f	3 s.f
C	Drug concentration in plasma at anytime	mean/SD/Geomean/CV/GeomeanSD/med = 4 s.f min/max = 3 s.f	same s.f as supplied from bioanalysis
C _{last}	Drug concentration at last observed time point	mean/SD/Geomean/CV/GeomeanSD/med = 4 s.f min/max = 3 s.f	same s.f as supplied from bioanalysis
C _{max}	Maximum observed plasma (peak) drug concentration	mean/SD/Geomean/CV/GeomeanSD/med = 4 s.f min/max = 3 s.f	same s.f as supplied from bioanalysis
C _{min}	Minimum observed plasma drug concentration	mean/SD/Geomean/CV/GeomeanSD/med = 4 s.f min/max = 3 s.f	same s.f as supplied from bioanalysis

Ctrough	Observed trough plasma drug concentration	mean/SD/Geomean/CV/GeomeanSD/med = 4 s.f min/max = 3 s.f	same s.f as supplied from bioanalysis
CL	Total body clearance of drug from plasma after intravascular administration	mean/SD/med = 4 s.f min/max = 3 s.f	3 s.f
CL/F	Apparent total body clearance of drug from plasma after extravascular administration	mean/SD/med = 4 s.f min/max = 3 s.f	3 s.f
CL _R	Renal clearance of drug from plasma	mean/SD/med = 4 s.f min/max = 3 s.f	3 s.f
λ_z	Terminal elimination rate constant	mean/SD/Geomean/mean/CV/SD/med = 5 s.f min/max = 3 s.f	4 s.f
F	Fraction of administered dose systemically available	mean/SD/Geomean/CV/CI/max/min as % to 2 d.p	as % to 2 d.p
F _{rel}	Fraction of administered dose systemically available relative to standard reference such as alternative formulation (note: not IV)	mean/SD/Geomean/CV/CI/max/min as % to 2 d.p	as % to 2 d.p
Fe	Fraction excreted unchanged in urine	mean/SD/med = 4 s.f min/max = 3 s.f	3 s.f
	Metabolite: parent ratio	Geomean/mean/CV/SD/med = 4 s.f min/max = 3 s.f	3 s.f
MRT	Mean residence time of the unchanged drug in the systemic circulation	mean/SD/med = 4 s.f min/max = 3 s.f	3 s.f
Rac	Accumulation ratio	Geomean/mean/CV/SD/med = 4 s.f min/max = 3 s.f	3 s.f

tlag	Time delay between drug administration and the first observed concentration in plasma	med = as actual time min/max = as actual time	same s.f as supplied
tmax	Time to reach peak or maximum observed concentration or response following drug administration	med = as actual time min/max = as actual time	same s.f as supplied
TCP	Temporal change parameter in systemic exposure (also known as: time dependency, temporal parameter change, linearity index)	Geomean/mean/CV/SD/med = 4 s.f min/max = 3 s.f	3 s.f
$t_{1/2}\lambda_z$	Half-life associated with terminal slope (λ_z) of a semi-logarithmic concentration-time curve	mean/SD/med = 4 s.f min/max = 3 s.f	3 s.f
Vss	Volume of distribution at steady state from a systemic dose	mean/SD/med = 4 s.f min/max = 3 s.f	3 s.f
Vss/F	Volume of distribution (apparent) at steady state	mean/SD/med = 4 s.f min/max = 3 s.f	3 s.f

N number included in summary table for all parameters as whole numbers

d.p = decimal places

s.f = significant figures

Note: Not all the above parameters may be applicable for this study.
